9.2. Site Principal Investigators

A principal investigator will lead operations at each enrollment site (Penn, Northwestern, and Corporal Michael J. Crescenz VAMC) and will be responsible for various aspects of the study, including data collection, adherence to all policies and procedures, and maintenance of study protocol to ensure that the specific objectives are being met. In conjunction with the Sponsor, they will oversee the safety of study participants. They will interact with the Sponsor team, including the Medical Director, the data management team, the study chair and the IND sponsor regulatory lead, as needed.

9.3. Investigators Committee

An Investigators Committee will hold a monthly call and discuss aspects of the study, including enrollment, retention, data management, quality assurance, and other issues as they arise. [name] will chair the committee, which will include the following members: [name], [name], [name], [name], and [name]. Minutes of these meetings will be distributed and kept on file. The study chair and the site PIs will have authority to make

decisions that require immediate attention when the committee is unavailable to meet. The study chair will adjudicate disagreements within the committee. The sponsor has the final responsibility for all study decisions.

9.4. Operational Affairs Committee

This committee will be responsible for oversight and coordination of the day-to-day activities of the project. Committee members will include the site PIs, the study coordinators at both enrollment sites, the post-doctoral researcher in charge of processing the MRI fat/water imaging, creatine-CEST and PC-MRI data, the echocardiography/tonometry quantification technician and staff members of the biostatistical team. This group, along with all of the members of the Investigators Committee, will hold an in-person meeting at the beginning of the project to review the study protocol and the policies and procedures for its implementation. Members of the Operational Affairs Committee will participate in the Investigators Committee, but may hold additional meetings/calls throughout the project to review subject recruitment, retention, data transfer, quality of data, etc. Minutes of these meetings will be distributed and kept on file.

9.5. Data Management

The UPENN site will serve as the data coordinating center (DCC) and will play a fundamental role in overseeing randomization, data entry, data coordination, data transfer, and DSMB meetings. [name] will be director of the DCC. Within the UPENN School of Nursing, DCC will have access to state-of-the-art computing resources capable of supporting studies ranging in size from one to more than 100,000 subjects. The equipment is fully supported by the Office of Technology and Information Systems (OTIS), which has complete business continuity and disaster recovery via redundant, distributed data centers and backup processes, in addition to traditional office and project management software.

The data for this trial will be collected in ad hoc source documents by the research staff during each study visit, using trial-specific and visit-specific data collection forms. All source documents collected in this trial will be housed inside of a locked cabinet in the offices of the research staff, located at each study site. Data capture and storage will be accomplished within the framework of the Research Electronic Data Capture (REDCap) project. REDCap is a secure, web-based application designed exclusively to support data capture for research studies. It provides an intuitive interface for data entry with data validation, audit trails for tracking data manipulation and export procedures, automated export procedures for seamless data downloads to common statistical packages, including SAS, and procedures for importing data from external sources. As of March 2015, REDCap was in production use or prototype build-status for more than 99,000 studies spanning numerous research focus areas across a consortium of 940 active institutional partners, including the University of Pennsylvania. Once the DCC launches the REDCap database into production mode, the study coordinators will be responsible for transmitting the participant coded electronic data using standardized data collection instruments to the database manager who will check the data for accuracy and completeness and follow-up with the research assistants as needed. The research coordinators will perform manual data entry from source documents and self-administered participant questionnaires (such as quality of life questionnaires), and the DCC will perform comprehensive data quality checks.

9.6. Quantification Core Laboratories

Various physiologic core laboratory units will be in charge of analyzing physiologic data from the trial.

9.6.1 Echocardiography Core Laboratory: The echocardiography core lab, directed by [name], has extensive experience in analyzing echocardiographic data for multicenter trials. The lab functions as the core lab for 2 ongoing international multicenter trials in heart failure (CVRx HOPE4HF and CVRx NeoHF) and one US-based multicenter study focused on HFpEF and HFrEF (BMS CV002004). The core lab has all the capabilities required for echocardiographic data management and quantification in this study. The core lab has well established standard procedures for receiving and logging imaging data, quantitative analyses, quality control, audit trails, and communication with study sites (queries about individual issues, feedback for quality control). The core lab will be responsible for generating and updating manuals for echocardiographic data acquisition, which will standardize procedures across the sites. The core lab will certify individual technicians performing measurements for the study after reviewing of sample scans (from normal volunteers) across the 2 sites, and will review and update certification as needed. The core lab will have the capacity to veto individual technicians from performing studies for the trial, based on data quality. The echocardiographic core lab will hold monthly calls with a representative of the data management core to discuss issues regarding core lab data management.

9.6.2 Arterial hemodynamics and exercise physiology core laboratory: The arterial hemodynamics core lab, directed by [name], has experience in analyzing hemodynamic data for various large cohort studies (MESA, Asklepios)^{83, 93, 95, 97, 142-145} and currently functions as the core lab for physiologic data for several ongoing multicenter studies (ACRIN 4008, BMS CV002004, iCAP study, CREST study). The core lab has specific experience in assessing specific exercise-related phenotypes relevant to inorganic nitrate effects¹⁰² and has adequate capabilities required for physiologic data management and quantification in this study. The core lab will have ad hoc teleconference calls with [name] (consultant in this grant). [name] will provide input about specific datasets in which there may be questions about physiologic phenomena. In addition to enhancing the interpretation of our human datasets, this will facilitate scientific interactions and will spark new ideas that will facilitate the translation of human observations to animal models and vice-versa. The physiology core lab will hold monthly calls with a representative of the data management core to discuss issues regarding core lab data management.

9.6.3 MRI core laboratory: The MRI quantification core lab will be directed by [name] and will include a designated post-doctoral researcher (35% effort throughout the grant duration) who will be in charge of implementing the scans, performing QC of data as the study progresses, and performing standardized quantification of MRI images. [name] laboratory has extensive experience in MRI quantification, with >100 publications in quantitative MRI and 14 completed studies using CEST imaging in the last 5 years.^{75, 126, 128, 146-155} The MRI core lab will hold monthly calls with a representative of the data management core to discuss issues regarding core lab data management.

9.6.4 Imaging data management: All imaging electronic data will be stored within a secure HIPAA-compliant network-attached storage server, and is accessible only to those who are specifically given access by the core lab director. The secure server has mechanisms for redundant storage and data backup at different physical locations, to prevent data loss from disasters (such as a fire).

9.6.5 Data Safety Monitoring Board: The DSMB will provide independent oversight of the project. The DSMB will be responsible for assessing: 1) baseline comparability between groups; 2) participant accrual rate and retention; 3) resource availability; 4) data quality with special emphasis on eligibility data; and 5) patient safety. The board will make recommendations regarding: study continuation, protocol modification, and review of additional data. The conference call meetings and progress reports will be set by the DSMB.

9.6.6 Cardiac MRI core laboratory: Cardiac MRI quantification will be supervised by [name], with support from [name]. [name] will have access to software available in [name] core laboratory, including CMR 42 software and Matlab software.

9.7 Conflict of Interest Management

[name] is named as inventor on a patent application which has been assigned to the University of Pennsylvania. This constitutes Clinical trial intellectual property (as defined under University of Pennsylvania policy) relevant to this trial. Therefore, the Offices of Research Services and Vice Provost for Research have formulated a management plan for [name] participation in the trial as Study Chair and Grant PI. Notification of thist management plan will be distributed to DSMB members, site PIs and Sub-Investigators and the operations of the trial will adhere to this plan.

10. STATISTICAL CONSIDERATIONS

10.1. Power calculations

We will randomize 84 subjects to one of 2 sequences (i), each of which consists of 2 periods (AB/BA design). We now have pilot data regarding the distribution of the changes in peak VO_2 (the primary endpoint of the study) as well as various secondary endpoints, among patients with HFpEF. We considered an increase in peak VO₂ of \sim 0.6 ml/kg/min to be the minimum clinically significant change. This was based on the fact that even "modest" changes of comparable magnitude in peak VO₂ have been associated with improved outcomes.¹⁵⁶ The standard deviation of the change in peak VO₂ in our pilot trial was 1.23 ml/kg/min. Therefore, the standardized effect size is 0.49 or greater. Assuming a 90% retention rate, enrolling 84 subjects in this cross-over trial will have 80% power to detect such an effect size in the intervention induced change of our study endpoints, with a two-sided α =0.05. Based on the distribution of the changes in study endpoints in our pilot trial or from repeated measurements of the Kansas City Cardiomyopathy Questionnaire in HFpEF patients, we estimated that this trial study is powered (80%) to detect the following changes in other endpoints: 4.6 points for the Kansas City Cardiomyopathy Questionnaire, 8.2% for exercise vasodilatory reserve, 19% for cardiac output reserve, 5 seconds for PCr/Cr recovery kinetics, and 4.2% change in reflection magnitude. We note that these differences are well below what is considered a clinically significant change in KCCQ (10 points or more, http://cvoutcomes.org/pages/3217) or the effect size that has been observed for these endpoints in our pilot trial.¹¹¹ Therefore, we are confident that we will achieve adequate power not only for our clinical endpoints, but also for our physiologic measures. PASS11157 was used to perform power analyses.

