6-week endpoint assessment: Following ~6-weeks of therapy with KNO₃/KCI, subjects will return for endpoint assessments. Physical examination with measurement of orthostatic blood pressure, pill count, KCCQ, dietary counseling, cognitive assessment, and side effect assessments will be performed. A urine pregnancy test will be performed in women with childbearing potential. An intravenous catheter will be placed in the antecubital vein and securely fixed in place. Blood, urine, and saliva samples will be collected prior to, and approximately 2 hours after the morning dose administration, given with a standardized low-nitrate breakfast. Blood RNA samples will be collected prior to the morning dose administration using Paxgene tubes (BD Biosciences, Franklin Lakes, NJ). Subjects will then undergo repeat echocardiography, arterial tonometry, and blood pressure measurements (including BP+ central blood pressure measurements). Subjects will then perform a maximal-effort peak oxygen consumption (VO₂) test using a supine bicycle exercise test with expired gas analysis. Cardiac output at rest will be measured immediately prior to exercise using pulsed wave Doppler echocardiography. Exercise cardiac outputs will also be obtained using the same technique. An additional blood sample will be obtained at peak exercise. The Aurora watch will be worn during exercise when possible. Subjects enrolled at Penn or the VA will undergo an assessment of skeletal muscle mitochondrial oxidative capacity using MRI either before, or at least 3 hours after, peak VO₂ testing. Based on scheduling and availability, the MRI may be performed on a different day than the exercise study. The Kansas City Cardiomyopathy Questionnaire (KCCQ) will be administered.

Phase 1: 6-week Visit Procedures

• Interim medical history, concomitant medications

- Physical exam (including orthostatic vital signs)
- Pill count
- Blood, urine and sputum collection, blinded drug administration
- ECG, labs (CBC, comprehensive metabolic panel, methemoglobin, pregnancy test as needed, BD PAXgene RNA samples)
- KCCQ
- Blood, urine, and saliva collection approximately 2 hours post-administration
- Cognitive assessment
- 2D echocardiogram, arterial tonometry

•Cardiopulmonary test with resting and exercise cardiac output measurements, blood draw at peak exercise

- If feasible, plantar flexor exercise / MRI (fat/water imaging / Creatine CEST / PC-MRI); these measurements are not performed at the Northwestern site

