10.2. Data Analysis Plan

The co-primary outcome variables will be peak VO₂ and work performed during a symptom-limited maximal effort exercise test. All secondary outcome measures are continuous variables. The predictor of interest for all aims will be intervention (KNO₃ therapy vs. placebo), with analyses based upon the total number of subjects randomized. Initial descriptive estimates of all measures will be generated for study participants at each time point by treatment group. Statistics will include estimates of central tendency, measures of variability, and derived moments of skewness and kurtosis. Analyses of distributional properties will be performed to determine if variance stabilizing or normalizing transformations should be applied. Outliers will be assessed via visual inspection of distributions and checked for accuracy. Aim 1 will assess the effects of potassium nitrate therapy on peak O_2 / work performed (co-primary outcomes) and quality of life score (secondary outcome). An initial assessment of the treatment effect will be performed using the paired t-test and the non-parametric Wilcoxon sign-rank test on the difference between the paired within subject outcome measures. This will be followed by a more comprehensive linear mixed-effects model analysis¹⁵⁸ allowing for assessments of the treatment effect on each continuous outcome of interest while controlling for effects of other covariates such as period, sequence, and a random subject effect nested within sequence. For non-normal distributed outcomes, we will utilize nonparametric methods or consider distribution-stabilizing transformations. The intervention groups will initially be compared within each period (time invariant covariates will only be compared for period 1) according to continuous covariates described above using parametric or non-parametric one-way ANOVA models, depending upon whether or not normality appears to be in question. Levine's tests will be used to assess homogeneity of variance. Additionally, the intervention groups will be compared within period according to categorical covariates using Fisher's Exact tests. Significant differences between groups on these variables will result in their use as control variables in the modeling of outcome. Separate models will be generated for each of the two outcome measures, with each outcome measure regressed on intervention group assignment, along with baseline outcome and any other covariates deemed prognostic in preliminary analyses. The linear mixed-effects models will incorporate adjustments for any period effect and include data from dropouts.¹⁵⁹⁻¹⁶¹ The model will include subject-specific intercepts as random effects, and assumes independent and identically distributed random errors within subject. Restricted maximum likelihood estimation will be used, and an appropriate covariance matrix will be specified. Model assumptions will be examined (eg,QQ plots to assess normally distributed residuals for valid Wald tests). All mixed-effects models will be analyzed using the SAS PROC MIXED procedure¹⁶² in SAS version 9.3 (SAS Institute, Inc., Cary, NC). We will make every possible effort to minimize missing data and ensure final assessments for participants opting to discontinue study participation. Missing data, however, is an inevitable problem in a longitudinal study. The mechanism for missingness-missing completely at random (MCAR), missing at random (MAR), nonignorable or not missing at random (NMAR)-will be evaluated prior to implementing methodology intended to minimize bias from missing data.¹⁶³ We anticipate that ~10% of randomized subjects will not complete the study.

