10.4 Cardiac MRI sub-study analysis and power calculations

The aim of this ancillary study is to assess the paired difference in myocardial blood flow and perfusion reserve in response to KNO₃ or the control intervention (KCI) in a cross-over design. We will therefore utilize paired-t tests to estimate the difference. The non-parametric Wilcoxon sign-rank test will be considered, as appropriate. For exploration of the relationship between MPR and myocardial fibrosis or myocardial function, we will compute Pearson's correlation coefficients for linear associations, or the Spearman's Rank Correlation coefficient for monotonic non-linear associations. A p-value less than 0.05 will be considered significant.

Power calculations: The standard deviation of the change in MPR in repeated measures in prior studies is 0.5. Assuming a dropout rate of 10% (effective n=18), the ancillary study will have 85% power to detect a standardized effect size of 0.75 or greater. Therefore, our study will be powered to detect an improvement of 0.375 in MPR with KNO₃ vs. KCl.

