16. APPENDIX 2. ANTICIPATED STUDY TIMELINE AND KEY DATES

	2015	2016	2017	2018	2019	2020
Creation of Case Report Forms						
Creation of Database						
Site activation, Penn						
Site activation, Northwestern						
Creation of Manual of Procedures						
Initial DSMB Meeting						
Kick off meeting						
Active randomization, Penn						
Active randomization, Northwestern						
Active follow-up						
Database Lock						
Design manuscript submission						
Primary Manuscript Preparation and submission						
Ancillary Manuscripts based on unblinded data						
Ancillary manuscripts and abstracts based on blinded measures						

KEY DATES

Date of 1st patient randomized	July-Aug, 2016			
Date of last patient randomized	September 1st, 2019			
Date of last patient follow-up visit	December 7th, 2019			
Date of data cleaned and ready for analysis	April 1st, 2020			
Final manuscript preparation	April-June 2020			
Projected date of publication	October 1st, 2020			
Patients randomized per year of the study				
	Penn	Northwestern	Cumulative	Minimal Enrollment
			Total	Target
Year 1	6	3	9	7
Year 2	16	12	37	28
Year 3	12	8	57	43
Year 4	12	7	76	57
Year 5	0	0	76*	76*
		20	70	76
Total	46	30	76	/0

17. APPENDIX 3 Instructions for wearing the Aurora Device (Pulse Watch)

The Aurora device is designed to record your pulse throughout the day. We ask that you wear throughout the day and night, as you may wear a watch. During your first study visit, we will do a demonstration to teach you how to place and secure the device to your wrist.

Use of the Aurora Device is very safe. However, there are a few precautions of which you should be aware:

The wrist strap will need to be moderately tight for acquisition of good quality pulse signals. It should never be so tight, however, as to restrict circulation in the hand. If you feel a tingling sensation in the hand or wrist where the Aurora device is being worn,

immediately loosen the wrist strap. If the sensation persists, take the device off and discontinue use.

- The device will beep several times during the day. When you hear the beep, you should touch the two contacts on the front of the device with two fingers from the hand that is not wearing the device, as illustrated in the following image:

- The device has been engineered to be robust to normal daily wear conditions, but it is not waterproof. Therefore, avoid submerging the device in water or using it outdoors in heavy rain.

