- e. Addition of standardized low nitrate breakfast to baseline visit following the blood draw for labs and biomarker samples.
- f. SpecificationSpecification of cutpoints for considering a quantitative G6PD activity test "positive" for clinically significant G6PD deficiency (<60% of normal).
- g. Increase of number of enrolled subjects to 84.

Version 10 (October 2018)

- a. Added laungage for recent FDA guidance regarding GBCA (Gadolinium Based Contrast Agent) administration. The potential risks associated with these procedures and adequacy to protect against these risks were also updated.
- b. Some minor typos and formatting errors were corrected.
- c. Clarification of the role of the DSMB and PI reporting requirements
- d. Clarification of some exclusion criteria.

Version 11 (March 2020)

a. Added [name], M. SC, to protocol as sub-investigator

Version 12 (07-Oct-2021)

a. Added clarification of consent procedure

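### Section 10.1 states 80% power for a 0.6 ml/kg/min difference in peak VO2, but its own inputs give about 99%; the error is conservative

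*Combined protocol and SAP*

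**What the plan says.** Section 10.1 sets about 0.6 ml/kg/min as the minimum clinically significant change in peak VO2. It then says that the SD of the change "in our pilot trial was 1.23 ml/kg/min. Therefore, the standardized effect size is 0.49 or greater". The conclusion drawn is: "Assuming a 90% retention rate, enrolling 84 subjects in this cross-over trial will have 80% power to detect such an effect size", at two-sided alpha 0.05. The same paragraph goes on to say that "this trial study is powered (80%) to detect the following changes in other endpoints", and lists KCCQ, exercise vasodilatory reserve, cardiac output reserve, PCr/Cr recovery and reflection magnitude without an SD for any of them.

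Section 10.2 plans a first test of the treatment effect "using the paired t-test and the non-parametric Wilcoxon sign-rank test on the difference between the paired within subject outcome measures", followed by a mixed model with period and sequence terms. It makes peak VO2 and total work co-primary and states no split of alpha.

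Section 10.4, for the cardiac MRI sub-study, takes an SD of the change in MPR of 0.5 and 18 completers, and says that "the ancillary study will have 85% power to detect a standardized effect size of 0.75 or greater".

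The accrual table in Appendix 2 ("Patients randomized per year of the study") totals 76. The entry for Version 9 in the history of changes reads: "Increase of number of enrolled subjects to 84".

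**The concern.** An effect size near 0.49 in a paired comparison needs only a few dozen pairs for 80% power. A claim of 80% with roughly 76 pairs is therefore out of line with the inputs beside it. Either the power is misstated, or 1.23 is not the quantity that the text calls it.

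This is the only power statement for a co-primary endpoint. As written, a reader of a neutral result would think that a true 0.6 effect had a 20% chance of being missed. The stated inputs put that chance at little more than 1%. The definition of the SD also decides how much room 84 subjects leave, for example for a stricter alpha. The secondary detectable differences carry the same 80% label and may share the problem.

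**Working it through.** **Inputs.** From Section 10.1: difference 0.6, SD of the change 1.23, 84 randomized, 90% retention, two-sided alpha 0.05. From Section 10.2: a paired t-test on within-subject differences.

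**Completers.** 84 × 0.90 = 75.6, so n = 75 or 76.

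**Effect size.** d = 0.6 / 1.23 = 0.488, which agrees with the stated 0.49.

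**Formula.** Power = P(T > t₀.₉₇₅), where T is noncentral t with n − 1 degrees of freedom and noncentrality d√n. For n = 76 the noncentrality is 0.488 × 8.718 = 4.25.

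**Step 1: does 80% reproduce at N = 84?** No.

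| Reading of 1.23 | n | Power for 0.6, alpha 0.05 | Power for 0.6, alpha 0.025 | Difference detectable at 80% (alpha 0.05) |
|---|---|---|---|---|
| SD of the paired difference | 75 | 98.6% | 97.2% | 0.403 |
| SD of the paired difference | 76 | 98.7% | 97.4% | 0.400 |
| Per-period within-subject SD (SD of difference 1.23 × √2 = 1.74) | 75 | 83.8% | 75.6% | 0.570 |
| Per-period within-subject SD | 76 | 84.3% | 76.3% | 0.566 |

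Using n − 2 degrees of freedom, as for a period-adjusted crossover test, leaves the paired figures unchanged to the precision shown. On the paired reading, 35 completers give 80.05%. The alpha 0.025 column is a sensitivity check only.

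**Step 2: how large could the SD be?** With 75 or 76 completers, 80% power for 0.6 is kept up to an SD of the change of 1.83 or 1.84, about 1.5 times the stated value.

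**Step 3: which SD does the plan use elsewhere?** In Section 10.4, d = 0.375 / 0.5 = 0.75 and n = 18. The paired formula gives 85.0%, exactly the stated figure. Treating 0.5 as a per-period SD (d = 0.75 / √2 = 0.53) gives 56%. So where the plan uses the same term a second time, it means the SD of the paired difference.

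**Step 4: check against the pilot.** Section 3.5.1 reports 12.6 against 11.6, a difference of 1.0, with P = 0.005. The pilot size is not stated. Assuming 14 to 19 pairs, a paired SD of 1.23 gives P from 0.009 to 0.002 (0.005 to 0.004 at 16 to 17 pairs), while a paired SD of 1.74 gives P from 0.05 to 0.02. The pilot result fits the paired reading.

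**Step 5: where could 80% come from?** On the per-period reading, 68 completers give 80.05%, and 76 × 0.90 = 68.4. Appendix 2 totals 76: Penn 6 + 16 + 12 + 12 = 46, Northwestern 3 + 12 + 8 + 7 = 30. This suggests a figure carried over from a sample size of 76, with an extra √2 on the SD. That is inference only, and the finding does not depend on it.

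**The case against.** The arithmetic mismatch is hard to dispute. The strongest reply is that it is harmless and that the corrected figure would be overconfident.

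- **Conservative error.** Power is understated and nothing in the conduct of the trial changes. This is true. It limits the seriousness but does not make the sentence correct.
- **Small pilot.** The 1.23 comes from a single-dose beetroot juice study in a population enrolled from one center, 88% male, which Section 3.5 itself calls small. Assuming 16 to 18 pairs, the upper 95% confidence limit for the SD is 1.90 to 1.84, where power for 0.6 falls to about 77% to 80%. This stands. Any restated power should be read beside the SD limit of about 1.84, because pilot uncertainty reaches it.
- **The per-period reading is not in the text.** Section 10.1 says SD of the change, and Section 10.4 and the pilot P value agree. This is right, and makes the paired figure the main result. The other branch is kept because it is the obvious candidate if the sponsor's own calculation used a different SD.
- **Wilcoxon test.** On the per-period reading, an assumed efficiency of 0.955 gives 82% to 83%, and 0.864 gives 78% to 79%, so 80% can be bracketed. That needs both a departure from the text and a pessimistic efficiency. On the paired reading the same efficiencies give 97% to 98%.
- **Total work.** Its adequacy at 84 cannot be checked, because Section 10.1 gives no target difference or SD of the change for it. This stands: keeping 84 is supported here for peak VO2 only.

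**Conclusion.** The concern holds. For the stated inputs and the planned paired test, power for 0.6 ml/kg/min is 98.6% to 98.7%, not 80%; 80% is reached at 0.40 ml/kg/min. This rests on 1.23 being the SD of the paired difference, as the text says, and on 75 or 76 completers. If it is a per-period SD, the paired t-test has 83.8% to 84.3% power and reaches 80% at 0.57, so the stated figure still does not follow.

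The error is conservative and does not threaten the trial. It should be corrected because it misdescribes the design for a co-primary endpoint. The minimum clinically significant change remains 0.6; the 0.40 describes sensitivity only. No figure is claimed for total work or the secondary endpoints.

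**What to change.** 1. Confirm from the pilot data whether 1.23 is the SD of the paired difference, and say so in Section 10.1.
2. If it is, replace the power sentence with: *With 84 randomized and about 76 completers, power is about 99% for 0.6 ml/kg/min (about 97% at alpha 0.025); 80% power is reached at 0.40 ml/kg/min; 80% power for 0.6 is kept up to an SD of the change of about 1.84.* If it is a per-period SD, state about 84% power for 0.6 and 80% power for 0.57.
3. Reconcile the Appendix 2 total of 76 with 84.
4. Recompute the secondary detectable differences at 84 randomized from the sponsor's actual SDs. For PCr/Cr recovery, count only subjects expected to have leg MRI: Section 5.3 says that "these measurements are not performed at the Northwestern site", and Section 4.3.2 allows subjects with MRI contraindications to enroll without the scans.

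Keep the sample size at 84. The cost is a rewording of Section 10.1 and an updated accrual table, with no change to enrolment or analysis.
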